3.1.1. Clinician administered measures

1. Montgomery Asberg Depression (MADRS)⁴⁹

- 2. Columbia Suicide Severity Rating Scale (C-SSRS)⁵⁰
- 3. Qualitative interview post-psilocybin

In-person screening visit. At the study screening visit, the study, the conditions, and the procedures involved, will be explained, and discussed with each subject. Each participant will have a chance to ask questions and to receive answers before making a final decision whether to participate. Participants who decide to participate will document their informed consent. For safety, after completing the consent, the participants may designate 2 adults who will be expected to have continuing contact with the subject, who may provide patient transportation, and who may observe changes in the participants' behavior and attitude that warrant notification of the research staff and/or PI. The screening visit will include the clinician-administered MADRS, and to be eligible for the study a MADRS score of 20 or greater is required.

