4.1. Inclusion Criteria

- a. Participants must be physicians or nurses or advance practice providers (nurse practitioners or physician assistants) with at least 1 month of frontline clinical experience during the COVID pandemic who rate at least 2 of 4 items from the COVID Exposure index as 'more than half the days' during their peak 2 week period of exposure:
 - i. Caring for someone critically ill with COVID-19, or who became critically ill while you were involved.
 - ii. Working longer hours than usual in order to provide assistance or care to individuals with COVID-19
 - iii. Witnessing or responding to a death related to COVID-19, or losing a patient you had been caring for to COVID-19
 - iv. Caring for patients who have died without family physically present due to COVID-19 precautions

- b. Have a Montgomery-Asberg clinician-administered depression score \geq 21, indicating moderately severe symptoms. This measurement is clinician-administered and will be performed by a study team member who is not a therapist, who will receive special training.
- c. Have had persistent symptoms despite at least one medication and/or therapy trial of standard care treatment for depression.
- d. English speaking able to understand the process of consent and the risk and benefits associated with the study, and able to give written informed consent.
- e. Must be willing to sign a medical release for the investigators to communicate directly with their therapist and doctors to confirm a medication and/or medical history. This is decided on a case by case basisupon the discretion of the PI.
- f. Must be driven home after the medication dosing session by a driver(which could be a friend, family, rideshare or taxi).
- g. Must provide at least one adult to have continuous contact with the participant, provide participant transportation, monitor changes in the participant's behavior, and notify research staff of behavior changes.
- h. Has been off selective serotonin inhibitors for five half-lives of the drug plus 2 weeks.
- i. Must avoid taking any psychiatric medications or starting a new psychiatric medication during the study. Should participant's doctor recommend starting a new psychiatric medication, participant will be required to notify the study team and the subject would withdraw from the study

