- j. Must provide a contact (relative, spouse, close friend, or other caregiver) who is willing and able to be reached by the Clinical Investigators in the event of a participant becoming suicidal.
- k. Must have a negative pregnancy test at study entry and prior to each medication dosing session if able to bear children and must agree to use adequate birth control.
- Are willing to commit to preparation sessions, medication dosing sessions, integration sessions, to complete evaluation instruments and commit to be contacted for all necessary telephone contacts.

4.2. Exclusion Criteria.

- a. Personal or immediate family history of schizophrenia, bipolar affective disorder, delusion disorder, paranoid disorder, or schizoaffective disorder.
- b. Suicidal ideation with a C-SSRS > 3
- c. Current substance abuse disorder (except in the case of mild alcohol use)
- d. Neuroleptic and SSRI medications that cannot be tapered and discontinued in conjunction with the participant's prescribing physician.
- e. Unstable neurological or medical condition; history of seizure, chronic/severe headaches.
- f. Positive urine pregnancy test at the time of screening
- g. Any unstable medical condition that my render study procedures unsafe based on the medical history performed as part of the screening procedures, including active cardiac medical issues such as ongoing angina, uncontrolled hypertension, or recent cardiac ischemia requiring medical attention (within the past 3 months
- h. Any use of psychedelic drugs within the prior 12 months.
- i. Use of tramadol, due to the potential for serotonin syndrome with concomitant use of

Page 23 Version 1.16, July 18, 2022

psilocybin.

- j. Allergy to niacin (N.B. the investigators will inform participants that flushing, redness, tingling, and headache are normal side effects that do not predict anaphylaxis, which although reported is extremely rare).
- k. Individuals who are on MOAI (monoamine oxidase inhibitors) or who have a known sensitivity to the drug or its metabolites. Psilocybin is contraindicated in medications that are known UGT (UDP-glucuronosyltransferase) enzymemodulators. The concurrent use of SSRI/SNRI meds is assumed to be contraindicated due to the potential to increase the risk of serotonin syndrome and/or to attenuate the binding of psilocin to the HT2A receptor.

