4.5. Participant Withdrawal or Termination

Participants may withdraw their consent for use of their data and/or terminate participation in the study at any moment during the study by calling the Principal Investigator or a member of the research team. To revoke authorization of the use and disclosure of Personal Health Information, the participant must follow-up the phone call by submitting a request in writing to the Principal Investigator. In this event, the Principal Investigator will indicate in the data base that consent from the participant is no longer active, and that data can no longer be used.

Page 24 Version 1.16, July 18, 2022

A participant may be withdrawn from the research for any of the following reasons:

- (1) A participant will be withdrawn if they become actively suicidal
- (2) A participant will be withdrawn if during the preparation visits, they show signs of severe personality disorder that was not evident in the screening visit.
- (3) A participant may be withdrawn if their withdrawal is in the best interests of either the participant or of the research (e.g., due to a medical condition making the procedures unsafe or any condition making interpretation of the results difficult).
- (4) A participant may be withdrawn if they are unable to comply with study visits (e.g., they miss their preparation visits without explanation).

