6.2. Study schedule for participants by visit

6.2.1. Screening and Informed consent

Prior to participation in this research, subjects will receive a brief secure online screening survey and then if eligible, will be screened by phone to determine preliminary eligibility. All subjects will be informed about the phone screening and what the screening process involves.

All potential participants will be told that we collect demographic information, relevant medical history, and psychiatric history during the screening process. Screening data are entered directly into a secure online database and are considered a source document.

All seemingly eligible subjects will be told that they need to come in for baseline screening visit, and will be informed about baseline questionnaires, clinician assessment, blood draw, and pregnancy test (if applicable) to ensure their eligibility. Subjects are free to decline participation at this point or to discontinue participation at any future point and to withdraw from consideration.

Some potential participants live in another state, and it may not be feasible to have them come for an in-person screening visit. In this case we will conduct the screening interview uligescure video communication platforms. We will ask these participants to send us their most recent physical, and blood work (recent as of 1 month from the screening visit will be allowed). This will be faxed to the PI and reviewed for potential participation. A remote urine test will be ordered for the screening process of remote participants.

Prior to obtaining informed consent, the PI will confirm that the participant meets all study inclusion and exclusion criteria. The investigator or research staff member obtaining consent will ask the participant to provide a brief summary of the study to ensure they understand what is being asked of them and any potential risks and benefits.

Note that if a female subject is pregnant, or breast-feeding, or does not agree to use an approved birth control method (i.e., oral, injectable, or implant birth control, condom, diaphragm with spermicide, intrauterine device, tubal ligation, abstinence, or partner with vasectomy) she will be excluded.

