6.2.3. Medication Dosing session (Visit 3)

Procedures for psilocybin administration and the conduct of the session will be similar to procedures used in studies with psilocybin conducted at New York University, Johns Hopkins, and Yale. Participants will be instructed to consume a low-fat breakfast before reporting to the clinic room for the psilocybin sessions. Before psilocybin administration, urine pregnancy test will be conducted in females of childbearing potential, and a negative pregnancy test will be required in order to continue in the medication session. Participants and staff will also complete pre-session questionnaires. Before each psilocybin session, study personnel will interview the participant. If the investigator believes that the session is contraindicated, the session will be cancelled or postponed.

Psilocybin will be administered in opaque gelatin capsules with approximately 100 ml water. At least one therapist, under the supervision of the investigators, will be present in the room and available to respond to participants' physical and emotional needs during the full course of the session (at least 7 hours). A physician on the study team will be immediately available via pager or mobile phone for at least 3 hours or until the peak effects of psilocybin have subsided, whichever is longer.

During the session, participants will lie on a couch, wear eyeshades, and listen to a program of music through headphones. The participant will be encouraged to focus her or his attention inward. The eyeshades and music are intended to encourage this inward reflection. Heart rate and blood pressure will be measured pre drug administration, at 30, 60, 90, 120 minutes after drug administration, and then at least hourly until at least 6 hours after drug administration and until drug effects have subsided. Heart rate and blood pressure assessments will be obtained after the participant has been sitting or recumbent for at least 5 minutes. Sessions are expected to last approximately 7 to 10 hours. A sample schedule for the medication dosing session is as follows:

Approximate Time	Procedure or Action
09:00	Urine pregnancy test for females of childbearing potential,
	participant acclimates to environment, completes measures.
09:30	Baseline BP, Pulse, Temp.
	Medication Administration.
	Begin video recording.
10:00	BP, Pulse
10:30	BP, Pulse
11:00	BP, Pulse
11:30	BP, Pulse
12:30	BP, Pulse
13:30	BP, Pulse
14:30	BP, Pulse
15:30	BP, Pulse
16:30	BP Pulse.

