	Assessment for discharge home.

At about the same time of each heart rate/blood pressure measurement, monitors will complete notations in the Medication Day Case Report Form to rate the presence and intensity of behaviors, signs, and reported symptoms, including sleepiness, amount of speech, anxiety, stimulation/arousal,

tearing/crying, nausea/vomiting, yawning, restlessness, feelings of unreality, visual changes, euphoria, and peacefulness. Video and audio recordings will be made throughout the session, as allowed by participants.

Participants will be encouraged to lie comfortably in bed wearing eye shades during the first few hours of the experience and to listen to pre-selected music chosen by the study staff. Two team members will remain with the participants the entire time and beavailable for any processing of intrapsychic material made manifest by the treatment.

If participants experience or report on any adverse effects or if the research staff feelsthat at the end of testing, that the participant has any adverse effects, participants will be asked / required to remain until effects wear off and medically cleared by the PI. Medical assistance will be offered. The investigators will query participants about suicidal ideation or intent during screening, and prior to each psilocybin session. Participants who evidence suicidal ideation or intent will be withdrawn from the study and referred to appropriate psychiatric care.

In the event that participants experience distressing anxious symptoms during the drug session, the clinical personnel in attendance (the principal investigator and team member) will initiate verbal communication designed to reorient and reassure that participant. The occurrence and intensity of anxiety or panic responses can be reduced through providing participants with information on potential drug effects, supervision, and monitoring of participants for the duration of drug effects. The goal in this study is to treat participants undergoing anxiety or panic reactions first by verbal and psychological interventions and using anxiolytic medication only after verbal and psychological interventions have failed, and if participants are endangering themselves or others. Residual symptoms will be addressed during the frequent follow-up psychotherapy visits with the investigators.

At the end of the medication dosing session:

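### The protocol gives two different MADRS entry cut-offs (20 and 21) and conflicting rules on whether a person with low-level suicidal ideation may enter and be dosed.

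*Combined protocol and SAP*

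**What the plan says.** **Depression severity.** Section 3.1.3, describing the in-person screening visit, states that "to be eligible for the study a MADRS score of 20 or greater is required". Criterion 4.1b sets the minimum on the clinician-administered scale at "21, indicating moderately severe symptoms". Section 6.2.1 adds that, before consent, "the PI will confirm that the participant meets all study inclusion and exclusion criteria".

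**Suicidality.** Three places set a rule.

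- Exclusion 4.2b: "Suicidal ideation with a C-SSRS > 3".
- Section 6.2.3: "The investigators will query participants about suicidal ideation or intent during screening, and prior to each psilocybin session". The next sentence reads: "Participants who evidence suicidal ideation or intent will be withdrawn from the study and referred to appropriate psychiatric care".
- Section 4.5, reason (1): "A participant will be withdrawn if they become actively suicidal".

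Section 6.2.3 also leaves room for judgement on the dosing day: "If the investigator believes that the session is contraindicated, the session will be cancelled or postponed".

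Around these rules sits a monitoring plan. The risk table in section 1.3.3.8 and the safety plan in section 6.5 provide for the C-SSRS throughout the study. Section 1.3.3.8 requires immediate notification of the PI, and arrangements for psychiatric evaluation, if suicidality increases. Section 6.4 makes a psychiatrist available when mood or suicidality changes significantly. Section 6.5 describes escalation to the PI or the emergency room when the assessor has serious concerns.

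**The concern.** An eligibility or withdrawal rule should give the same answer wherever a staff member reads it. Here the screening procedure and the criteria list differ by one point on the scale that also carries the primary endpoint. More importantly, the entry exclusion and the dosing-visit rule give opposite answers for the same person with low-level ideation.

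The second conflict is the one that matters. Such cases are foreseeable: section 4.1 requires at least moderately severe depression and symptoms that have persisted despite a trial of treatment, and section 3.1.4 requires participants on antidepressants to stop them. If staff follow different sections, similar people could be admitted and dosed in one case and withdrawn in another. The same question returns for placebo participants, who are re-screened before open-label psilocybin under sections 6.1 and 6.3.

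**Working it through.** The plan states no figure on this point that could be recomputed, so the check is a comparison of the rules.

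**Step 1: MADRS.** Both rules concern the clinician-administered scale and the same entry decision. Scores that satisfy 20 or more but not 21 or more are {20}, which is one value. A candidate must pass every criterion at the PI's check in section 6.2.1, so the two rules together reduce to 21 or more, and the expected number entering at exactly 20 is 0. The value of 19 in the phone pre-screen belongs to the self-rated MADRS-S. It is only a guide to likely eligibility and is not a third cut-off.

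**Step 2: suicidality.** Each rule is applied literally at the stage it covers.

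| Situation | 4.2b (entry) | 4.5(1) (after entry) | 6.2.3 (screening and before each session) |
|---|---|---|---|
| Screening, C-SSRS above 3 | Excluded | Not applicable | Withdrawn |
| Screening, ideation scored 3 or less | Not excluded | Not applicable | Withdrawn |
| Before dosing, ideation scored 3 or less | Entry rule, already passed | Withdrawn only if judged to meet its undefined term | Withdrawn |

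The first row agrees. The second is a direct contradiction, because 6.2.3 expressly covers screening and carries no severity threshold. In the third row, 6.2.3 again requires withdrawal of someone whom 4.2b admitted and whom 4.5(1) need not remove.

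**Step 3: do the other safety provisions settle it?** The trigger in section 1.3.3.8 is an increase in suicidality, and section 6.4 refers to a significant change. A participant whose ideation is low and stable meets neither. Section 6.5 acts on the assessor's serious concerns and leads to further contact or emergency care. None of the three states whether a person with stable low-level ideation may enter or be dosed. The power in 6.2.3 to cancel or postpone a session lets a clinician hold back, but it does not say which rule applies.

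**Step 4: consequence for the statistics.** The sample-size table in section 9.2 depends on group size, significance level, power and an effect in SD units. With 15 per group and two-sided 0.05, the noncentral t calculation gives detectable effects of 1.06 SD at 80% power and 1.23 SD at 90%, as the plan states. For drop-out, 30 / (1 − 0.15) = 35.3, rounded up to 36, also as stated. Neither threshold is an input to these figures.

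**The case against.** The strongest reply is that entry and withdrawal rules may properly differ because they act at different stages, and that the protocol surrounds both with close monitoring. Much of this stands.

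- A reader might infer three irreconcilable suicidality standards. The text does not support that. Exclusion 4.2b works at entry, and 4.5(1) covers deterioration afterwards, so those two can coexist. The conflict comes from 6.2.3, which spans both stages.
- A reader might infer that low-level ideation goes unmonitored, or is assessed without an instrument or an action rule. Section 6.5 specifies the C-SSRS at all study visits, and section 1.3.3.8 sets a response to any measured increase. What is missing is a consistent rule for entry and dosing.
- A reader might infer that open-label re-screening has no defined criteria. The natural meaning in sections 6.1 and 6.3 is the list in Section 4. That list imports the same conflict, because 4.2b would apply again alongside 6.2.3.
- Section 1.3.3.8 refers to a detailed therapist manual, which is not among the documents. It may give staff a working threshold. The point is therefore confined to what the protocol states.

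The stage argument fails for 6.2.3 itself. Its query is made at screening, where 4.2b also applies, and the two give different answers on the same day.

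**Conclusion.** Both contradictions stand on the current text and should be corrected.

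The MADRS mismatch is a wording error at one step: one score value, with no expected entrants at that value while the PI's check is carried out as described. It would be wrong to infer that people are being enrolled below the criterion.

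The suicidality conflict is a real inconsistency in a safety rule. It affects anyone with ideation scored 3 or less at screening or before dosing. How many people that is cannot be estimated, because the documents give no rate of ideation in this population. It rests on reading 4.2b as leaving scores of 3 or less admissible, as its wording does, and on reading 6.2.3 literally, since it has no severity qualifier. A reader might also infer that the stricter rule governs by default. The protocol does not say so, and its only numerical criterion points the other way, so the choice belongs to the study clinicians.

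No power, sample-size or test result changes.

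**What to change.** 1. In section 3.1.3, change the screening MADRS requirement from 20 to 21.
2. Have the study clinicians choose one C-SSRS threshold and state it in both 4.2b and 6.2.3.
3. Define the term in 4.5(1) on the same scale, so that the post-entry rule can be applied consistently.
4. State that the threshold is assessed before randomisation and again before the capsule is given. The section 3.1 schedule already has a C-SSRS at every visit, so no visit is added.
5. State in sections 6.1 and 6.3 that the same threshold applies at open-label re-screening.

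The cost is one clinical decision, amendment wording in those sections and matching screening forms.

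There is a trade-off. If the stricter rule is chosen, some people now admissible under 4.2b become screen failures. Section 6.2.1 places randomisation at the end of visit 2, so ideation first found on the dosing day would lead to withdrawal after randomisation but before dosing. Section 9.2 specifies an intent-to-treat primary analysis and allows for 36 − 30 = 6 non-completers, and such withdrawals would draw on that allowance. Assessing before randomisation limits this but cannot remove it. The documents give no rate from which to count either loss.

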3.1.4. Study Research Evaluations and Procedures

Medication and lifestyle changes may be required of all participants. All participants will be required to taper off and discontinue use of antidepressants (such as SSRIs) before starting the study and cannot take antidepressants during the study even if they were taking them before study entry. Participants who were taking antidepressants before

study entry will need to be off them for five half-lives of the drug plus 2 weeks before starting the study and will be required to stay off their medication until after they have completed the primary outcome measurements on day 28. After unblinding (as early as day 28, after primary outcome measurements are received). Subjects who were randomized to psilocybin will be able to resume antidepressants in consultation with their provider. Subjects who were randomized to placebo will need to stay off their antidepressants if they wish to have an open-label psilocybin medication session, and after their open-label psilocybin session they will need to stay off their medication until at least day 29 post-open-label-psilocybin, until after they have completed the day 28 post-open-label-psilocybin outcome measurements. If a participant randomized to placebo does not wish to have an open-label psilocybin medication session, they will be able to resume their antidepressants after their primary outcome measurements in consultation with their provider, as early as day 29 post-open-label-psilocybin. They will also need to abstain from tobacco products, alcohol, or any recreational drugs such as marijuana during the study. Study personnel may obtain a release to contact the participant's prescribing provider to discuss current prescriptions and medication history. This is decided on a case by case basis upon the discretion of the PI.

Medication contraindications will include anti-seizure medications, insulin and oral hypoglycemics, hypertension medications that act on the central nervous system (clonidine and aldomet specifically), cardiovascular medications and the following psychotropic medications: anti-psychotics (first and second generation agents), anti-depressants and mood stabilizers. Psychotropic medications cannot be taken in the previous two weeks, with Prozac (fluoxetine) not being taken within the last 5 weeks prior to receiving any study agents. Participants may only take prn (as needed) benzodiazepines (i.e., lorazepam) up to three days before the session. Participants will refrain from taking any medications the day of either the experimental psilocybin medication dosing or active-placebo-control medication dosing session, except prescribed opiate pain medication or over-the-counter non-narcotic pain medication at any time. It will also be necessary to refrain from drinking alcoholic beverages the day before, the day of, and the day after each medication dosing session.

Physical exam, and blood and urine tests are required at the screening visit to meet eligibility criteria. As part of the study participants will have a physical examination, and screening blood (including a comprehensive metabolic panel, chemistries, hematological tests) and screening urine toxicology tests (for medications as described in Section 1.3.3.8; and pregnancy for female participants of childbearing potential). These results will also become part of the research case record.

Randomization and One-time Administration of the Study Medications Psilocybin or active- placebo-control Niacin. Psilocybin and niacin (active-placebo-control agent) will be administered in identically appearing opaque capsules with approximately 180ml of water. The dose of psilocybin will be 25 mg, which has been recently demonstrated to be as effective as a body weight-adjusted dose. Fee The dose of niacin will be 100 mg, and GMP niacin will be provided by the Usona Institute. In the study, half of the participants will be randomized to receive psilocybin (n=15) or the active-placebo-control, niacin (n=15). Following the first treatment session of either the active agent or active-placebo-control, participants who were randomized to receive active-placebo-control will be offered the option to receive open-label psilocybin. (The blind will be broken after Day 28 to make this determination; this is after our primary endpoint which is collected on Day 28. The study rater (for clinician-administered measures) Wremain blinded to the treatment assignment. Data will be collected from all subjects after open-label treatment for descriptive purposes, but these data will not be analyzed as part of our primary analysis plan.

Page 21 Version 1.16, July 18, 2022

Clinical Assessments and Study Evaluations. Online surveys and measures will be offered using secure data capture systems, using online or paper documents. These evaluations will include self-report questionnaires and clinician administered measures. This testing may last up to 1 to 2.5 hours.

Research study measures, follow-ups and assessments are outlined (in Tables below) and represent study specific clinician administered and self-administered measures. Safety measures and checks will be completed at some study visits: vital signs, adverse events, spontaneously reported reactions, general well-being, medications, and changes to any medications.

All participant responses to measures and assessments will be recorded either on traditional paper formats and scanned to a secure server, or in online data capturing systems which instantly upload responses or surveys to a secure server. All portable digital participant data will be uploaded immediately and stored in secure databases, on password-protected computers in locked offices, and on secure servers.

